10.1.1.1.2 Study Site Visit 2 (Week 4 / D29 ± 7 days)

This visit includes:

- On-site visit.
- EQ-5D patient questionnaire
- IMP/NIMP compliance check including diet therapy (Patients should be on a diet following JAS guideline or equivalent).
- Vital signs: heart rate and sitting SBP and DBP.
- Record of all concomitant medications including CV medications.
- Collection of adverse events including CV events (if any).
- Fasting blood sample listed below will be collected and measured.
 - Hematology and chemistry.
 - TC, calculated and directly measured LDL-C, HDL-C, TG, non-HDL-C (central laboratory).

Note: Additional blood samples can be obtained for measurement of above listed items and others at the study site by Investigator's judgment as needed.

- When the Investigator or the site medical staff confirms all required measurements are completed, the patient in the alirocumab arm will receive Praluent® administration.
- The patient should be observed for at least 30 minutes after Praluent® administration.
- If patient is in the SoC arm, ongoing LMTs will be continued unless modification of LMTs is made by the Investigator's medical judgment.
- For the patient in the alirocumab arm, an appointment will be given for next Praluent® administration visit (Week 6 / D43).
- For the patient in the SoC arm, an appointment will be given for the first phone-call interview (Week 8 / D57).

10.1.1.1.3 Study Site Visit 3 (Week 12 / D85 ± 7 days)

This visit includes:

- On-site visit.
- EQ-5D patient questionnaire.
- IMP/NIMP compliance check including diet therapy (Patients should be on a diet following JAS guideline or equivalent).
- Body weight.
- Vital signs: heart rate and sitting SBP and DBP.
- Record of all concomitant medications including CV medications.
- Collection of adverse events including CV events (if any).
- Fasting blood sample listed below will be collected and measured.
 - Hematology and chemistry.
 - TC, calculated and directly measured LDL-C, HDL-C, TG, non-HDL-C (central laboratory).
 - HbA1c (central laboratory).

Note: Additional blood samples can be obtained for measurement of above listed items and others at the study site by Investigator's judgment as needed.

- When the Investigator or the site medical staff confirms all required measurements are completed, the patient in the alirocumab arm will receive Praluent® administration.
- The patient should be observed for at least 30 minutes after Praluent® administration.
- If patient is in the SoC arm, ongoing LMTs will be continued unless modification of LMTs is made by the Investigator's medical judgment.
- For the patient in the alirocumab arm, an appointment will be given for next Praluent® administration visit (Week 14 / D99).

- For the patient in the SoC arm, an appointment will be given for next phone-call interview (Week 16 / D113).

10.1.1.1.4 Study Site Visit 4 (Week 24 / D169 ± 7 days)

This visit includes:

- On-site visit.
- EQ-5D patient questionnaire.
- IMP/NIMP compliance check including diet therapy (Patients should be on a diet following JAS guideline or equivalent).
- Body weight.
- Vital signs: heart rate and sitting SBP and DBP.
- Record of all concomitant medications including CV medications.
- Collection of adverse events including CV events (if any).
- Fasting blood sample listed below will be collected and measured.
 - Hematology and chemistry.
 - TC, calculated and directly measured LDL-C, HDL-C, TG, non-HDL-C (central laboratory).
 - HbA1c (central laboratory).

Note: Additional blood samples can be obtained for measurement of above listed items and others at the study site by Investigator's judgment as needed.

- When the Investigator or the site medical staff confirms all required measurements are completed, the patient in the alirocumab arm will receive Praluent® administration.
- The patient should be observed for at least 30 minutes after Praluent® administration.
- If patient is in the SoC arm, ongoing LMTs will be continued unless modification of LMTs is made by the Investigator's medical judgment.
- For the patient in the alirocumab arm, an appointment will be given for next Praluent® administration visit (Week 26 / D183).
- For the patient in the SoC arm, an appointment will be given for next phone-call interview (Week 28 / D197).
- The Investigator should make a schedule with the patient for the evaluation IVUS study at the EOT (Week 36 ± 2 weeks) by this on-site study visit if possible.

10.1.1.1.5 Study Site Visit 5 (End of Treatment Visit, Week 36 / D253 ± 14 days)

This study visit includes:

- On-site visit.

- Contact the registration center to document the end of study.

Note: If the evaluation IVUS imaging is completed in this visit, EOT will be the end of study. If the evaluation IVUS imaging is scheduled after this visit, the contact with the registration center will be made when the evaluation IVUS imaging has been completed and this point is considered the end of study.

- EQ-5D patient questionnaire.
- IMP/NIMP compliance check including diet therapy (Patients should be on a diet following JAS guideline or equivalent).
- Body weight.
- Vital signs: heart rate and sitting SBP and DBP.
- Record of all concomitant medications including CV medications.
- Collection of adverse events including CV events (if any).
- Urine pregnancy tests (WOCBP).
- Fasting blood sample listed below will be collected and measured.
 - Hematology and chemistry.
 - TC, calculated and directly measured LDL-C, HDL-C, TG, non-HDL-C (central laboratory).
 - Apo B, Apo A-1, Apo B/Apo A-1, Lp(a) (central laboratory).
 - HbA1c (central laboratory).
 - hs-CRP (central laboratory).
 - Hepatitis C virus antibody levels (central laboratory).

Note: Additional blood samples can be obtained for measurement of above listed items and others at the study site by Investigator's judgment as needed.

- If patient is in the SoC arm, ongoing LMTs will be continued unless modification of LMTs is made by the Investigator's medical judgment.
- Evaluation IVUS study should be performed out by this visit \pm 14 days and the IVUS images are transferred to the central reading laboratory immediately after the IVUS study.
- The notification of the end of study should be communicated to the registration center.

10.1.1.2 Praluent® administration visit (alirocumab arm only)

When patients are randomized to the alirocumab arm, they have to visit the study sites every 2 weeks for Praluent® administration in addition to on-site visits as indicated below:

- Week 2 / D15 \pm 7 days
- Week 6 / D43 \pm 7 days

- Week 8 / D57 \pm 7 days: IMP/NIMP compliance recording including diet therapy (based on JAS guideline or the equivalent)
- Week 10 / D71 \pm 7 days
- Week 14 / D99 \pm 7 days
- Week 16 / D113 \pm 7 days: IMP/NIMP compliance recording including diet therapy (based on JAS guideline or the equivalent)
- Week 18 / D127 \pm 7 days
- Week 20 / D141 \pm 7 days: IMP/NIMP compliance recording including diet therapy (based on JAS guideline or the equivalent)
- Week 22 / D155 \pm 7 days
- Week 26 / D183 \pm 7 days
- Week 28 / D197 \pm 7 days: IMP/NIMP compliance recording including diet therapy (based on JAS guideline or the equivalent)
- Week 30 / D211 \pm 7 days
- Week 32 / D225 \pm 7 days: IMP/NIMP compliance recording including diet therapy (based on JAS guideline or the equivalent)
- Week 34 / D239 \pm 7 days

Note: IMP/NIMP compliance, diet therapy and AE/SAE will be assessed and recorded at Week 8, Week 16, Week 20, Week 28, and Week 32 as indicated above.

Note 2: During Praluent® injection visits at Week 2, Week 10, Week 22, and Week 34, the appointment will be given for next on-site visits (Week 4, Week 12, Week 24, and Week 36, respectively). The patient should be instructed to visit the study site in the morning under fasting conditions, which is defined as an overnight fasting no less than 8 hours that consist of no food or liquid intake, other than water unless exception made by Investigator's medical judgment.

10.1.1.3 Phone-call interview (SoC arm only)

When patients are randomized to the SoC arm, they will have phone-call interview every 4 weeks for NIMPs compliance including diet therapy, CV medications, and AE/SAE recording in addition to on-site visits as indicated below:

- Week 8 / D57 \pm 7 days
- Week 16 / D113 \pm 7 days
- Week 20 / D141 \pm 7 days
- Week 28 / D197 \pm 7 days

- Week 32 / D225 ± 7 days

Note: During the phone-call interviews at Week 8, Week 20, and Week 32, the appointment will be given for next on-site visits (Week 12, Week 24, and Week 36, respectively). The patient should be instructed to visit the study site in the morning under fasting conditions, which is defined as an overnight fasting no less than 8 hours that consist of no food or liquid intake, other than water unless exception made by Investigator's medical judgment.

10.2 DEFINITION OF SOURCE DATA

Evaluations that are reported in the e-CRF must be supported by appropriately signed identified source documentation related but not limited to the following:

- Agreement, date, and signature of informed consent mentioning the study identification.
- Patient identification, last participation in a clinical trial, medical history, associated disease, and data related to the studied pathology.
- Contraception methods for women of childbearing potential.
- Previous and concomitant medication (including the LMT).
- Study identification.
- Treatment number, dates of administration.
- Dates of visit and assessments including the examination report.
- Vital signs, height, body weight.
- Central laboratory reports (dated and signed by the Investigator or sub-Investigator).
- Laboratory values at study site (dated and signed by the Investigator or sub-Investigator)
- The registration center confirmation reports (randomization, discontinuation, and the end of the study).
- ECG records with physician's signature and dated.
- AEs and follow-up:
 - In case of SAE, the study site should file as the source document at least copies of the hospitalization reports and any relevant examination reports documenting the follow up of the SAE.
- Date of premature study discontinuation (if any) and reasons.

Source documentation may be found in the followings:

- Patient's identity.
- Medical history.
- Hospital records.
- Nursing notes.

- Physician's notes.
- Laboratory reports.

10.3 HANDLING OF PATIENT TEMPORARY OR PERAMENANT TREATMENT DISCONTINUATION AND OF PATIENT STUDY DISCONTINUATION

Study treatment should be continued whenever possible. In case the treatment is discontinued, it should be determined whether the discontinuation can be made temporarily; permanent treatment discontinuation should be a last resort. Any treatment discontinuation should be fully documented in the Case Report Form (CRF). In any case, the patient should remain in the study as long as possible.

10.3.1 Temporary treatment discontinuation

Temporary treatment discontinuation may be considered by the Investigator/sub-Investigator because of suspected AEs. Reinitiation of treatment will be done under close and appropriate clinical/and or laboratory monitoring once the Investigator/sub-Investigator will have considered according to his/her best medical judgment that the responsibility of the study treatment in the occurrence of the concerned event was unlikely and if the selection criteria for the study are still met (refer to Sections 7.1 and 7.2).

All treatment interruption duration should be recorded by the Investigator/sub-Investigator in the appropriate e-CRF screens when considered as confirmed.

Treatment interruption is defined as one or more scheduled injections that are not administered to the patient as decided by the Investigator/sub-Investigator.

10.3.2 Permanent treatment discontinuation with investigational medicinal product(s)

Permanent treatment discontinuation is any treatment discontinuation associated with the definitive decision from the Investigator or the patient not to re-expose the patient to the IMP at any time.

10.3.3 List of criteria for permanent treatment discontinuation (SoC or IMP)

The patients may withdraw from study treatment if they decide to do so, at any time and irrespective of the reason, or this may be the Investigator's decision. Patient withdrawal from the study treatment or study should be avoided as much as possible. All efforts should be made to document the reasons for treatment discontinuation and this should be documented in the e-CRF.

Patients should discontinue the study treatment for the following reasons:

- Pregnancy, intention for pregnancy, or no longer taking an effective contraceptive method (in female patients).
- Acute injection-site reaction of clinical concern.

- SAE (or non-serious but severe in intensity) of hypersensitivity reaction considered to be related to study treatment.
- At patient's request.
- If, in the Investigator/sub-Investigator's opinion, continuation of the study treatment is detrimental to the patient's well-being.
- Condition that requires discontinuation of study treatment (e.g., laboratory abnormalities, refer to decision tree Appendix F).
- At the specific request of the Sponsor.
- At the specific request of the Investigator with Sponsor's agreement.

Criteria of permanent treatment discontinuation due to insufficient adherence to medications are defined as followed:

- Alirocumab arm: IMP administration compliance is less than 50% for 12 weeks (3 months from the randomization visit).
- SoC arm: NIMP administration compliance is less than 50% for 6 months from the randomization visit.

Note for SoC arm: If patients exhibit their NIMP administration compliance is less than 50% for the first 3 months after the randomization visit, Investigators/sub-Investigator can terminate the study based on their judgment considering patients' safety.

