10.3.4 Handling of patients after permanent treatment discontinuation (SoC or IMP)

- All definitive discontinuation of study treatment should be recorded by the Investigator in the appropriate screens of the e-CRF and in the patient's medical records when considered as confirmed. The registration center should be notified when a patient prematurely discontinues the study. Patients should be asked to stick to the visit schedule for measuring laboratory test values until the end of study (Week 36).
- When patients permanently discontinue the study (regardless of the reasons) before Week 24 (6 months), they will have an unscheduled on-site visit as soon as possible (preferably within 7 days from treatment discontinuation) with assessments originally planned at the EOT visit (Week 36).
- When patients in the alirocumab arm permanently discontinue the study (regardless of the reasons) on Week 24 (6 months) or after, the Investigator should make the best effort to schedule the evaluation IVUS imaging with assessments originally planned at the EOT visit (Week 36) within 2 weeks from the last IMP administration (the earliest last IMP administration occurs on Week 22). If the patients decline the evaluation IVUS imaging after the study discontinuation, they will have an unscheduled on-site visit as soon as possible (preferably within 7 days from treatment discontinuation) with assessments originally planned at the EOT visit (Week 36).
- When patients in the SoC arm permanently discontinue the study (regardless of the reasons) on Week 24 (6 months) or after, the Investigator should make the best effort to

schedule the evaluation IVUS imaging with assessments originally planned at the EOT visit (Week 36) within 2 weeks from the determination date of the study discontinuation. If the patients decline the evaluation IVUS imaging after the study discontinuation, they will have an unscheduled on-site visit as soon as possible (preferably within 7 days from treatment discontinuation) with assessments originally planned at the EOT visit (Week 36).

- When patients, who develop AEs including AESIs and/or SAEs and need to be followed up as specified in this protocol, permanently discontinue the study, they will be followed up until recovery or stabilization of the AEs.

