### **2.3.1 Efficacy populations**

#### **2.3.1.1 *Modified intent-to-treat population***

The primary efficacy analysis population will be the modified intent-to-treat (mITT) population, defined as the randomized population who took at least one dose or part of dose of study drug, and has 2 analyzable normalized TAV, as defined below.

- One assessed before randomization
- Another one assessed after 24 weeks of treatment.

Patients in the mITT population will be analyzed according to the treatment group allocated by randomization.

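### The adherence stopping rules fall on opposite sides of Week 24, and only the later (SoC) stop leads by default to an IVUS that can count for the primary endpoint

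*Protocol*

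**What the plan says.** **Stopping for poor adherence (Protocol 10.3.3).** The criteria differ by arm in what they measure and when they apply: "Alirocumab arm: IMP administration compliance is less than 50% for 12 weeks (3 months from the randomization visit", and "SoC arm: NIMP administration compliance is less than 50% for 6 months from the randomization visit". For SoC patients who are already below 50% over the first 3 months, a note adds that "Investigators/sub-Investigator can terminate the study based on their judgment", with patient safety in mind.

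**Handling after a stop (Protocol 10.3.4).** Before the split: "When patients permanently discontinue the study (regardless of the reasons) before Week 24 (6 months), they will have an unscheduled on-site visit", preferably within 7 days, with the end-of-treatment assessments. After it, for SoC: "When patients in the SoC arm permanently discontinue the study (regardless of the reasons) on Week 24 (6 months) or after", the investigator makes a best effort to obtain the evaluation IVUS within 2 weeks, and the patient may decline. The matching alirocumab bullet also starts at Week 24 and states that the earliest last injection in that route is at Week 22. A general bullet covers all treatment stops: "Patients should be asked to stick to the visit schedule for measuring laboratory test values until the end of study (Week 36".

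**Staying in the study (opening of Protocol 10.3).** "In any case, the patient should remain in the study as long as possible".

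**Who is analyzed.** The mITT population needs two analyzable normalized TAV values, the second described as "Another one assessed after 24 weeks of treatment" (SAP 2.3.1.1; similar wording in Protocol 9.1.1 and 11.3.1.1). SAP 2.1.3.1 asks for at least 24 weeks of treatment and also for an image in the Week 36 window. SAP Table 3 opens that window at Day 169, counted from randomization. SAP 2.4.4.1 makes the mITT ANCOVA the main result.

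**The concern.** Whether a patient contributes to the primary endpoint depends on being imaged on Day 169 or later. The alirocumab adherence stop comes well before that day and the SoC stop comes on or after it. The instructions for what follows therefore lead towards a usable image in one arm and not in the other.

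Missing TAV would then be related both to treatment arm and to adherence. Blinded central reading does not help, because the problem is who is imaged and not how the image is read. The normalized TAV and PAV endpoints come from the same images, so both confirmatory tests are exposed.

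**Working it through.** **1. The plan's own figure.** A two-sample t-test with difference 8, SD 15 and two-sided 5% (Protocol 11.1) has power 90.06% with 75 per arm, and 150/(1 - 0.25) = 200. The sample size reproduces. The 25% non-evaluable allowance is not split by arm.

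**2. The rules in study days** (randomization is Day 1; SAP 2.5.1 sets a month at 30.4375 days).

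| Event | Week count | Month count |
|---|---|---|
| Alirocumab stop | 12 x 7 + 1 = Day 85 | 3 x 30.4375 + 1 = Day 92 |
| SoC stop | 24 x 7 + 1 = Day 169 | 6 x 30.4375 + 1 = Day 184 |
| IVUS window opens | Day 169 | Day 169 |

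The alirocumab stop precedes the window by 169 - 92 = 77 to 169 - 85 = 84 days. The SoC stop falls on its first day or up to 15 days after it.

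**3. What imaging follows.** After the SoC stop, a best-effort IVUS within 2 weeks would count. After the alirocumab stop, the pre-Week-24 bullet gives a visit within about 7 days, and any image then is too early. The post-Week-24 alirocumab bullet does not reach this patient, and the bullet asking for visits to Week 36 names only laboratory values. No text schedules a countable IVUS, and no text forbids one.

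**4. Would a later image qualify?** Read literally, 24 weeks of treatment excludes a patient stopped at Week 12. Four other places point the other way:
- Table 3 counts from randomization.
- SAP 1.6 records that the on-treatment condition was removed from mITT.
- SAP 2.3.1.2 lists poor adherence, and imaging outside Weeks 34-38 in the efficacy treatment period, as deviations that do not exclude from mITT.
- Protocol 10.3 keeps patients in the study.

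The question is open on the text.

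**5. Possible size (assumptions, not document figures).** Let a share p of each arm be non-adherent. Adherent patients have the planned 8-point benefit and non-adherent alirocumab patients have none. Non-adherers in both arms do worse by d points for other reasons. All non-adherent alirocumab patients are lost and all non-adherent SoC patients are imaged. With m the mean change in adherent SoC patients:
- All randomized: (m + pd) - [(1 - p)(m - 8) + p(m + d)] = 8(1 - p)
- As analyzed: (m + pd) - (m - 8) = 8 + pd
- Overstatement: p(8 + d)

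| p | d = 0 | d = 8 |
|---|---|---|
| 2% | 0.16 | 0.32 |
| 5% | 0.40 | 0.80 |
| 10% | 0.80 | 1.60 |

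The 8p part comes from losing alirocumab non-adherers at all. If SoC non-adherers were lost too, the analyzed difference would be m - (m - 8) = 8, still 8p too large. Only pd is due to the arms being handled differently. If lost patients keep half the drug effect, 8p becomes 4p.

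The pd part also arises with no drug effect. With d = 8, SD 15, and 75(1 - p) against 75 patients, the false difference is 0.16, 0.4 and 0.8 points at p = 2%, 5% and 10%. The two-sided rejection rate is 5.05%, 5.29% and 6.15% against a nominal 5%.

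**6. The planned safeguard.** SAP 2.4.4.1 imputes missing TAV in the randomized population. The listed variables include treatment group, baseline TAV and baseline characteristics, but not adherence or discontinuation. Stopped alirocumab patients would be imputed much like completers in their arm, so the correction is partial.

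**The case against.** A reader might infer that poorly adherent alirocumab patients leave the primary analysis by rule while equally non-adherent SoC patients stay in it. The documents do not support that, for four reasons:
- Section 10.3.3 stops study treatment. The pre-Week-24 bullet in 10.3.4 is worded for patients who discontinue the study, and 10.3 wants patients kept in. The SAP provisions in step 4 suggest that poor adherers and off-treatment images belong in mITT. The closing note of 10.3.4 also foresees images taken more than 2 weeks after the last injection.
- The behaviours are not the same. One rule counts injections and the other counts background medication. No listed adherence criterion covers statin compliance in the alirocumab arm.
- SoC patients need not stay. They can be stopped at 3 months on safety judgment, the later IVUS is best effort, and it can be declined.
- The size depends on chosen inputs. The nearest document figure, from the Japanese phase 3 study in Protocol Section 4, suggests a small p. There, 140 patients received alirocumab at Week 12, out of about 143 (10 patients reported as 7.0%). So 3/143, or about 2%, were off drug. That population differs, and the count omits poor adherers still on drug.

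All four points stand, and they limit the claim. They do not remove the difference in default imaging. Section 10.3.4 is headed as covering treatment discontinuation while its bullets speak of leaving the study, so a site could reasonably treat the two as one and not image the Week 12 stopper.

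**Conclusion.** The concern holds as an arm-dependent route to missing primary-endpoint data, made worse by an ambiguous mITT condition. It does not hold as exclusion by rule.

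The timing difference is certain from the text. Its effect is not, because the documents give no non-adherence rate. Under the assumptions in the working, with d from 0 to 8, the overstatement is 2-4% of the planned 8 points at p = 2% and 5-20% at p = 5-10%. It is smaller if partial dosing keeps some benefit, if some stopped alirocumab patients are imaged later, or if SoC non-adherers with d above zero are also missed. The direction towards alirocumab also rests on the assumptions: p(8 + d) turns negative if d is below -8.

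**What to change.** - Reconcile Protocol 10.3, 10.3.3, 10.3.4 and 11.3.1.1 with SAP 2.1.3.1, 2.3.1.1 and Table 3, so that stopping treatment and leaving the study are kept apart. The adherence thresholds, their timing and the safety-based termination remain the sponsor's decision.
- State that the already planned evaluation IVUS is sought on Day 169 or later, with Weeks 34-38 as target, in both arms. This applies to every consenting patient who stops study treatment early but remains in the study.
- Define the 24 weeks as time since randomization wherever the condition appears, and analyze these patients as randomized.
- Report missing evaluation IVUS by arm and reason.
- Include treatment discontinuation in the missing-data sensitivity analysis.

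**Cost.** A few sentences in a protocol amendment and an SAP revision. The imaging is already planned, and Protocol Section 4 describes follow-up angiography at 8-10 months as standard procedure in Japan. A few poorly adherent patients would enter mITT, so the estimated effect may be slightly smaller. With 75 imaged per arm and an effect of 8(1 - p), which is 7.84, 7.6 or 7.2 at p = 2%, 5% or 10%, power is 88.9%, 86.9% or 83.2%. The change has to be made during conduct, since images not acquired cannot be recovered at analysis.
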